
 Obtain oral consent for brief screening using Einstein Committee on Clinical Investigations (IRB) screening consent template Brief screen in private room in methadone clinic to determine eligibility Discuss study procedures, risks and benefits of study participation Obtain written consent for 1) clinical trial participation; 2) study staff to use protected health information from methadone clinic records; 3) study staff to disclose protected health information in event of psychiatric distress
Methadone clinic chart review:

 Laboratory test results: HCV Ab, HCV viral load, HIV (within 1 year), HCV genotype/subtype, IL28B, APRI and FibroSURE (biomarker tests for liver fibrosis) Methadone clinic attendance and dose
Second screening visit (medical eligibility determination by [name]):

 Review of HCV-related labs (as above) and fibroscan or liver biopsy (if available) Review of HCV Treatment Evaluation Flow Sheet to confirm no previous HCV treatment and planned on-site treatment regimen: fixed dose (sofosbuvir and ledipasvir) Participants who meet all eligibility criteria scheduled for a baseline visit Randomization (stratified, blocked) generated by centralized computer program

D.6. Participant tracking and retention. We have extensive experience following HCV- and HIV-infected drug users in studies. In our ongoing RCT of directly observed HCV treatment, 24 week follow-up was 92%.¹²⁹ In our completed RCT of directly observed HAART, 24-week follow-up was 86%.¹⁴² At enrollment and subsequent visits, we will record: 1) participants' address, phone number, and social security number; 2) contact information of family or friends; 3) contact information of participants' community-based organizations; 4) contact information of case managers; and 5) locations where participants "hang out".

D.7. Randomization. We will recruit 150 patients (100 on fixed-dose sofosbuvir and ledipasvir), with patients randomized to mDOT, CGT, or TAU in a 1:1:1 ratio (50 subjects in each group) in variable block sizes of 3-6 via central, computer-generated randomization. Two special randomization strategies (stratification and blocking) will be used to avert imbalances in prognostic factors, and to ensure comparison

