groups of approximately equal size. Because of the historical importance of IL28B genotype and stage of liver disease (cirrhosis v. no cirrhosis) in determining virologic outcomes,⁴⁶ we will stratify by these 2 factors. All subjects will have the IL28B genetic test performed as per our standard clinical algorithm. To determine presence of cirrhosis, all subjects will have 2 biomarker tests (APRI and Fibrosure) performed at baseline,¹⁴³⁻¹⁴⁴ per our standard clinical algorithm (Appendices A and D). Liver biopsy / Fibroscan is not required but will be performed if 1) biomarker tests are inconclusive for determination of cirrhosis as per the SAFE algorithm (<20%),¹⁴⁵ 2) to rule out co-occurring liver disease, or 3) if the result will influence the decision to initiate treatment. Results of liver biopsy / Fibroscan (if done) will be used for stratification instead of biomarker tests. Since IL28B explains much of the variability in response between African Americans and non-African Americans,^{96,146} and rates of SVR with DAAs may be equivalent in Latinos and non-Latino Whites,⁴⁶ we will not stratify by race or ethnicity, but will adjust in the analyses if necessary.

D.8. Treatment arms: TAU, mDOT, and CGT. All 3 models of care include co-located on-site care including HCV care, primary care, and substance abuse treatment. Table 2 summarizes similarities and differences between the 3 models. Subjects randomized to TAU will receive all medications monthly at the clinic from the clinic nurse, packaged in 7-day blister packs (oral medications)

Table 2: Element	IMB Model	TAU	mDOT	CGT
Co-located care	Information Motivation	X	X	X
Enhanced social support by providers	Motivation		Nurse – individual	Medical provider - group
DOT Interferon	Behavioral Skills		Nurse - individual	Medical provider - group
DOT telaprevir and ribavirin	Behavioral Skills		DAA 1-6 doses/week	
DOT snack (if telaprevir or RBV only)	Behavioral Skills		Nurse - individual	
Enhanced social support by patients	Motivation			Peers – group
Enhanced education	Information			Weekly educational sessions
Enhanced side effect management	Information Motivation		Nurse - individual	Weekly group treatment

D.8.1. Intensive treatment intervention arms (mDOT and CGT)

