D.11. Analytic plan. First, the success of randomization will be checked by comparing the mDOT, CGT and TAU groups on key variables, such as age, gender, ethnicity, race, HCV viral load, HCV subtype (1a vs. 1b), BMI, psychiatric history, active drug use, and social support.⁴⁶ By design, IL28B and stage of liver disease will be represented equally in each arm. Continuous variables will be compared between arms using the ANOVA or Kruskal-Wallis test, and categorical variables will be compared using chi-square or Fisher's exact tests. Variables that are not equally distributed will be included in multivariate models. In primary analysis, we will use the intention-to-treat principle, which preserves the advantages of a randomized design.

D.12.1. Hypotheses for Aim 1. We hypothesize that in the intensive intervention arms, compared to the control arm, rates of adherence, treatment completion, and SVR will be significantly higher, and that rates of resistance will be lower. We further hypothesize that the proportion of subjects in the intensive models of care arms who achieve an SVR will be equivalent to that observed in large registration trials.

D.12.2. Analytic plan for Aim 1. Adherence to DAAs, ribavirin, and IFN will be determined using electronic monitors and self report, as described above. Initially, adherence will be calculated as a single outcome for each subject, evaluated at the end of the study. We will use Chi-square tests or Fisher's exact test to compare the proportion of subjects who achieve high adherence rate ($\geq 80\%$) complete treatment, achieve SVR, and develop resistance in the three arms (mDOT, CGT, and TAU). If the omnibus equality test of adherence across the 3 groups is rejected, we will conduct the following 2 specific post-hoc pairwise tests with a Bonferroni adjusted 2-sided alpha= 0.025: mDOT vs. control, and CGT vs. control. This strategy will be applied to multivariable logistic regressions if any potential confounding variables not equally distributed between the study arms at baseline are identified.

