For the analysis of repeatedly measured adherence (using 6 post-baseline time points and adherence as a continuous measure), we will apply mixed effects linear model to test if the 3 groups are significantly different. This model accounts for within-subject longitudinal outcome correlation by taking the subject-level intercept as random. The model will include potential confounding variables. If the omnibus equality test is rejected, we will conduct the 2 post-hoc pairwise tests described above. Concerning potential clustering effects in the CGT arm, we used pilot data (5 groups) to examine whether clustering influenced adherence. Between cluster variation was not significant, as tested by application of a random effects repeated-measure ANOVA model. Clustering in the GCT arm will be minimal, and we will not adjust for it in statistical or power analysis.

We will also apply mixed effects logistic regression to test the significance of mDOT and CGT on repeatedly-measured undetectable HCV VL throughout the intervention period, adjusting for substance use. Changes in illicit drug use will be analyzed using urine toxicology data from each visit, counting the “person-month” as a unit of analysis, and analyzing the proportion of person-months that are positive for use of illicit drugs using a chi-square analysis.

As secondary analyses, we will examine if mDOT and CGT effects, v. TAU, will be mediated by IMB components. We will assess IMB model mediators of adherence at baseline, and during the intervention, and will analyze changes in those variables from the baseline to the intervention period. The indirect effects of IMB mediators will be tested by assessing changes in coefficients of the intervention effect (mDOT or CGT) with and without IMB component(s) in mixed effects models. Confidence intervals of the mediated effects will be calculated by bootstrapping, and mediation assumed if confidence intervals do not include zero.

D.12.3. Hypotheses for Aim 2. We hypothesize that only a minority (~20%) of IDUs will develop resistance, and that the relationship between adherence and resistance will be quadratic.

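### Randomisation is stratified by IL28B and cirrhosis, but the SVR comparison ignores those strata; if they are prognostic for SVR, the test is conservative and gives up a little power

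*Combined protocol and SAP*

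**What the plan says.** D.7 (Randomization) gives the reason for stratifying: "Because of the historical importance of IL28B genotype and stage of liver disease (cirrhosis v. no cirrhosis) in determining virologic outcomes". It continues: "we will stratify by these 2 factors". Allocation is 1:1:1 "in variable block sizes of 3-6 via central, computer-generated randomization".

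D.11 (Analytic plan) lists the baseline variables to be compared between arms and sets the two strata apart from that check: "By design, IL28B and stage of liver disease will be represented equally in each arm". The rule for covariates follows: "Variables that are not equally distributed will be included in multivariate models".

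D.12.2 (Analytic plan for Aim 1) specifies simple tests for adherence, completion, SVR and resistance across the three arms: "We will use Chi-square tests or Fisher's exact test to compare the proportion of subjects". Adjusted analysis is conditional on imbalance: "This strategy will be applied to multivariable logistic regressions if any potential confounding variables not equally distributed" between arms at baseline are found. The repeated-adherence model is looser: "The model will include potential confounding variables", with none named. The repeated viral-load model is adjusted for substance use. Neither model names IL28B or cirrhosis.

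**The concern.** The two factors that the sponsor singled out as important for virologic outcome are used to allocate patients and then dropped from the SVR comparison. The covariate rule selects on observed imbalance, and stratified blocking is meant to prevent imbalance in exactly these two factors, so the rule passes over them.

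Stratified allocation removes between-stratum variation from the difference between arms. An unstratified chi-square still counts that variation in its denominator. If the strata predict SVR, the test rejects less often than its nominal level, and the precision that the stratification could have given is not collected. D.9.3 treats virological response as the outcome that matters most clinically, and D.13 (Power considerations) expects a smaller effect with the current regimen, so unused precision is worth recovering.

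**Working it through.** **1. The plan's own power.** Inputs from D.13: 40 completers per arm and SVR of 70%, 70% and 40%. The omnibus alpha is not stated; 0.05 is assumed. The mean rate is 0.60. For the 2-df chi-square, λ = n·Σ(pᵢ − p̄)² / [p̄(1 − p̄)] = 40 × (0.1² + 0.1² + 0.2²) / (0.6 × 0.4) = 40 × 0.06 / 0.24 = 10. Power is 81.5%, which agrees with the stated figure of above 80%. No stratum adjustment is needed to reach it.

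**2. True size of the unstratified test.** With allocation balanced within strata, only within-stratum variance W = Σ wₛpₛ(1 − pₛ) contributes to arm differences, while the test divides by p̄(1 − p̄). Under the null the statistic behaves like R times a 2-df chi-square, with R = W / [p̄(1 − p̄)]. Since P(χ² > x) = exp(−x/2) for 2 df, the true size is 0.05^(1/R).

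Assumptions not in the documents: 30% C/C, 20% cirrhosis (independent), IL28B split as C/C v. other, and the prognostic odds ratios. The weights are then 0.3 × 0.2 = 0.06 (C/C, cirrhosis), 0.3 × 0.8 = 0.24 (C/C, none), 0.7 × 0.2 = 0.14 (other, cirrhosis) and 0.7 × 0.8 = 0.56 (other, none). The common null rate is 60%.

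Worked case, odds ratios 4 (C/C) and 0.33 (cirrhosis): stratum SVR is 0.634, 0.840, 0.302 and 0.568, averaging 0.60. W = 0.06×0.634×0.366 + 0.24×0.840×0.160 + 0.14×0.302×0.698 + 0.56×0.568×0.432 = 0.2131. R = 0.2131/0.24 = 0.888, and size = 0.05^(1/0.888) = 3.4%.

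| Odds ratios (C/C, cirrhosis) | Stratum SVR under the null | R | Size by formula | Size simulated | SVR power, unstratified v. stratified | Forgone |
|---|---|---|---|---|---|---|
| 1, 1 | 0.600 in all | 1 | 5.0% | – | 82.0% v. 81.9% | none |
| 2, 0.5 | 0.587, 0.740, 0.416, 0.587 | 0.960 | 4.4% | 4.4–4.5% | 82.4% v. 83.4% | 1.0 |
| 3, 0.4 | 0.618, 0.802, 0.350, 0.574 | 0.921 | 3.9% | 3.8–3.9% | 82.6% v. 84.7% | 2.1 |
| 4, 0.33 | 0.634, 0.840, 0.302, 0.568 | 0.888 | 3.4% | 3.2–3.4% | 83.0% v. 86.4% | 3.4 |

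Power is from 200,000 simulated trials per row, 40 per arm, SVR 70/70/40, allocation exact within strata. It compares the Pearson chi-square with a 2-df stratified Cochran-Mantel-Haenszel (CMH) statistic. The size range covers repeat simulations; the stratified test held about 4.8–4.9%.

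**3. With the plan's blocking.** Permuted blocks of 3 or 6 within four strata, N = 120, 30% C/C and an assumed 25% cirrhosis (8,000 trials per case) gave the same pattern. Power was 82.2% v. 82.2% when both odds ratios were 1.5 (inverted for cirrhosis), and 82.7% v. 86.2% at 4 and 1/3, where size was 3.3% v. 4.6%.

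**4. Pairwise SVR test at 0.025.** Simulated power rises from 70.4% to 73.1% at odds ratios 3 and 0.4, and from 70.6% to 74.5% at 4 and 0.33.

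**5. SVR near 95%.** D.9.6 cites SVR above 95% for the current regimen. At a common 95%, the two tests have nearly equal size (3.1–3.9% v. 3.3–4.0%). At an assumed 95/95/80, with 150 randomised and 20% attrition (6,000 trials per case), power is 60.1% v. 60.1%, 60.7% v. 61.0% and 59.9% v. 61.1% for the three prognostic scenarios. A further simulation put the gain at about 1–2 points.

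**6. Are such odds ratios plausible?** The documents give none for IL28B or cirrhosis. B.5 reports interferon-era SVR by race and ethnicity: 19% v. 52%, an odds ratio of (0.52/0.48)/(0.19/0.81) = 4.6, and 34% v. 49%, (0.49/0.51)/(0.34/0.66) = 1.9. It attributes much of such differences to variation near the interferon lambda 3 gene. That is indirect support, for older regimens only.

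**The case against.** The strongest reply is that nothing the plan claims is wrong. Unstratified power is 82–83% in every 70/70/40 scenario and does not fall as the strata become more prognostic. The error is on the safe side: no bias and no excess of false positives. The prognostic effects are assumed. D.7 itself speaks of historical importance, and B.5 ties IL28B to response under interferon and ribavirin. About 100 of the 150 participants are to receive the current regimen, where the gain nearly vanishes. All of this stands, and it limits the size of the point.

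It can also be said that the covariate rule does not bar the strata. It says which variables will enter, not that others may not; the adherence model has an open-ended list of confounders; and Table 3 lists IL28B and the fibrosis biomarkers among the covariate measures. That is fair for the models. It does not help the simple chi-square or Fisher test of SVR, which has no covariates.

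A reader might extend the point to adherence, completion and resistance. The documents do not support that: the stratification rationale concerns virologic outcomes, nothing links either factor to pill-taking or completion, and D.13 calls the resistance comparison underpowered and exploratory. A reader might also infer that confidence intervals for Aim 1 differences will be too wide, but the plan specifies no between-arm interval for an Aim 1 proportion.

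Finally, forcing both factors into every logistic model has a cost. At 95% SVR there would be about 6 to 8 failures in all (5% of 120 is 6; 5% of 150 is 7.5). Separation becomes a real risk, and the logistic estimand changes from a marginal to a conditional odds ratio.

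**Conclusion.** The mismatch between design and analysis is real and is firmest for the SVR comparison. Its consequence is conditional. If IL28B and cirrhosis predict SVR, the nominal 5% omnibus test runs at about 4.4% down to 3.2–3.4%, and about 1 to 3.5 points of power are forgone, for odds ratios from 2 and 0.5 to 4 and 0.33. These figures rest on the assumed 30% C/C, 20% cirrhosis, 40 per arm and SVR of 70/70/40. The loss is nil if the strata are not prognostic and about 1–2 points or less when SVR is near 95%.

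Two stronger readings are tempting and do not hold. One is that the tests are conservative and underpowered as a matter of fact; the documents give no prognostic effect for either factor under the current regimen. The other is that the stated SVR power fails; it reproduces at 81.5% without any adjustment. What is lost is additional precision that could be had at almost no cost.

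**What to change.** In D.12.2, prespecify the SVR omnibus test and the two comparisons with control as CMH tests stratified by the randomisation strata (IL28B by cirrhosis), and report Mantel-Haenszel risk differences. Include IL28B and cirrhosis in the repeated viral-load model regardless of observed balance, and exempt both from the imbalance rule in D.11.

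State in advance how sparse strata will be collapsed. Under the assumed frequencies the C/C-with-cirrhosis stratum holds about 0.06 × 120 = 7 completers, between 2 and 3 per arm. State also how IL28B is split for stratification, since D.7 does not say.

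Stratifying the adherence, completion and resistance tests in the same way is optional, for consistency; no gain is documented.

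The cost is SAP wording. D.7 has IL28B and the cirrhosis biomarkers obtained for all subjects as part of routine care and uses them for stratification, so no new data are needed.

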D.9.6. Future developments in HCV treatment. Study participants will receive state-of-the-art treatment (IFN in combination with telaprevir and ribavirin). As additional regimens become available with either more convenient dosing, fewer side effects, or increased efficacy, participants in all 3 arms will receive treatment according to best available practices. On October 10, 2014, the FDA approved fixed-dose (ledipasvir and sofosbuvir). Because rates of SVR are >95% in patients initiating treatment with fixed-dose (ledipasvir and sofosbuvir), all newly enrolled subjects will initiate treatment with this regimen. It is likely that our intensive models of care will be generalizable to IFN-sparing regimens which include only oral therapies. We recognize that HCV treatment has been greatly simplified, but issues with adherence, resistance, side effects, and cost will remain.

D.10. Data sources and collection.

D.10.1. Overview. Sources of data will include: blood and urine tests, participant interviews, medical charts, staff activity and expense logs, direct observation of staff, and electronic adherence monitors (Table 3).

D.10.2. Research visits. Research visits will occur at baseline, then every 4 weeks during the first 12 weeks of treatment, then at week 24 (if necessary), a “Final Treatment Week visit” will be conducted after the last day of treatment, and then post-treatment visits after 4, 12, and 24 weeks, for a total of up to 9 research visits. Participants will receive \$25 for each visit and an additional \$20 for visits with blood draws.

Baseline visit (Table 3). At baseline we will assess: sociodemographic and HCV clinical factors, potential mediating variables based on the IMB model, potential moderators (including psychiatric status, substance use, and unstable housing), and additional psychosocial factors hypothesized to predict adherence. The baseline visit will take approximately 3 hours. Blood will be collected at the first visit and stored for possible HCV viral load and resistance testing, and for future studies.

Follow-up visits (Table 3). Follow up visits will occur at weeks 4, 8, 12, and 24 (if necessary).

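### The Aim 1 SVR test pools two regimen eras without stratifying, and the baseline-imbalance rule will almost never bring regimen in: a loss of efficiency, not bias, whose size rests on assumed rates

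*Combined protocol and SAP*

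**What the plan says.** For the binary Aim 1 outcomes, D.12.2 states: "We will use Chi-square tests or Fisher's exact test to compare the proportion of subjects" with high adherence, completion, SVR and resistance. D.11 sets the covariate rule: "Variables that are not equally distributed will be included in multivariate models". D.12.2 repeats it for regression: "This strategy will be applied to multivariable logistic regressions if any potential confounding variables not equally distributed between the study arms at baseline are identified". The variables to be checked are introduced by an open 'such as' list that does not name regimen, and no threshold for imbalance is given.

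D.7 plans a mixed population: "We will recruit 150 patients (100 on fixed-dose sofosbuvir and ledipasvir", with 1:1:1 allocation "in variable block sizes of 3-6 via central, computer-generated randomization". Stratification is by IL28B and cirrhosis only. D.9.6 ties regimen to calendar time: after the October 2014 approval, "all newly enrolled subjects will initiate treatment with this regimen". The same section puts SVR on that regimen above 95%, and B.3 gives 75% for telaprevir-based therapy in a registration trial. D.13 plans SVR of 70% in both intensive arms against 40% or less in the control arm (TAU), claims power above 80%, and adds that the effect on ledipasvir/sofosbuvir is likely to be lower.

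**The concern.** Adjustment for a covariate gains power when the covariate predicts the outcome, whether or not the arms differ on it. A rule that admits covariates only when they are unbalanced therefore selects on the wrong property. Regimen is the clearest case here: the documents expect it to be related to SVR, and the design nearly guarantees that it is balanced. Pooling then leaves the between-regimen spread of SVR in the error term. At stake are the power and the interval width for SVR, in a trial whose D.9.3 ranks virological outcome as the most important clinical outcome and whose planned SVR power is only just above 80%.

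**Working it through.** **1. The plan's own power.** Inputs from D.13: SVR 70/70/40 (mDOT/CGT/TAU), 40 completers per arm, 2-df omnibus test. Overall alpha is not stated; 0.05 is assumed. Mean rate = 0.60. Noncentrality = 40 × (0.10² + 0.10² + 0.20²) / (0.60 × 0.40) = 40 × 0.06 / 0.24 = 10. Power = 81.5% (82.2% by simulation). The stated figure reproduces.

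**2. Would the imbalance rule pick up regimen?** Take 50 per arm and 50 of 150 on earlier regimens. The chi-square statistic for regimen by arm is Σd² / (50 × 1/3 × 2/3) = Σd² / 11.11, where d is each arm's departure from 16.67.
- p < 0.05 needs Σd² ≥ 5.99 × 11.11 = 66.6.
- At the switch, each of the four IL28B-by-cirrhosis strata (both factors taken as binary) has at most one open block. In the worst case, an open block of 6 in every stratum leaves two arms 8 ahead of the third: d = 2.67, 2.67, −5.33 and Σd² = 42.7. That cannot reach p < 0.05.
- In simulation, regimen was flagged in 0 of 20,000 trials at p < 0.05, 0.10 and 0.20. After 20% random attrition it was flagged in 0.005%, 0.08% and 0.6%.
- If regimen were unrelated to enrolment order, it would be flagged about 5% of the time at p < 0.05.

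**3. Variance of the SVR risk difference.** With weights 1/3 (earlier) and 2/3 (new), each arm contributes p̄(1 − p̄) unstratified, where p̄ = p_E/3 + 2p_N/3. Stratified, it contributes p_E(1 − p_E)/3 + 2p_N(1 − p_N)/3. Example: earlier 70 v 40, new 95 v 75.
- Intensive arm: p̄ = 0.8667; 0.1156 unstratified, 0.1017 stratified.
- TAU: p̄ = 0.6333; 0.2322 unstratified, 0.2050 stratified.
- Ratio = 0.3478 / 0.3067 = 1.13, equivalent to 13% more participants.

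**4. Power.** The design is 20,000 simulated trials per row: the first 50 enrolled on earlier regimens and the next 100 on the new one, stratified blocks of 3 or 6, and 120 retained at random. The tests are the 2-df Pearson chi-square and the 2-df Cochran-Mantel-Haenszel (CMH) test by regimen, alpha 0.05. Earlier-regimen rates are set at 70/70/40; all new-regimen rates are assumptions. Gains were taken before rounding.

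| New-regimen SVR, mDOT/CGT/TAU | Chi-square | CMH | Gain, points | Variance ratio |
|---|---|---|---|---|
| 70/70/40 (not prognostic) | 0.822 | 0.816 | −0.6 | 1.00 |
| 95/95/55 | 0.978 | 0.983 | +0.5 | 1.05 |
| 95/95/65 | 0.915 | 0.932 | +1.6 | 1.08 |
| 95/95/75 | 0.743 | 0.791 | +4.9 | 1.13 |
| 95/95/80 | 0.611 | 0.672 | +6.1 | 1.17 |
| 95/95/85 | 0.469 | 0.542 | +7.3 | 1.22 |
| 95/95/90 | 0.318 | 0.392 | +7.4 | 1.29 |
| 95/95/95 | 0.187 | 0.259 | +7.2 | 1.38 |
| 97/97/85 | 0.553 | 0.642 | +8.9 | 1.24 |
| 97/97/90 | 0.394 | 0.494 | +10.0 | 1.31 |

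Other rates move the gain both ways.
- Smaller: new 90/90/70 gives +3.1 and 85/85/70 gives +1.7; earlier 75/75/50 with new 95/95/75 gives +2.9.
- Overall rates held at 70/70/40 with regimen gaps of 20, 30 and 40 points: +1, +3 and +5.
- Over the 42 cells of a wider grid with chi-square power of 75% to 90%: median +4, maximum +12.
- Larger: gaps of 50 and 55 points at 70/70/40 overall give +8 and +10. A 50-point gap implies earlier-regimen SVR of 0.70 − (2/3)(0.50) = 37% and 0.40 − (2/3)(0.50) = 7%, far below the planned rates. Earlier 45/45/14 with new 95/95/75 gives +17, but the 14% in the documents is a liver-clinic figure for interferon and ribavirin, not on-site triple therapy.

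**5. Size under the null.** With SVR 55% v 95% by regimen and no arm effect, the chi-square rejects in 1.9% to 3.0% of trials across separate simulations. CMH rejects in about 5%.

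**6. Other outcomes.**
- Completion (earlier 60/85/50): 0.745 v 0.761 at new 80/95/75, and 0.472 v 0.519 at 90/95/85.
- Adherence (earlier 80/80/50): 0.747 v 0.753 at 90/90/70, and 0.482 v 0.494 at 90/90/80.

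**The case against.** An unadjusted test in a blocked randomised trial is valid, and the plan does not bar regimen: its list is open and no threshold is set. No primary outcome is named; adherence comes first in D.12.2 and D.13, and there the gain is negligible. The 95% figure is not a rate for this population: B.5 allows for real-world differences, and the introduction expects lower adherence and high discontinuation in injection drug users. The 70/70/40 rates are given for the trial as a whole, so assigning them to the earlier regimens is an interpretation.

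All of this stands, and it limits the size of the point. What it does not answer is that a choice left open until balance has been seen is not pre-specified, and that the stated criterion points away from the variable most worth including.

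There is also a textual obstacle. Table 1 makes starting ledipasvir/sofosbuvir an inclusion criterion, and the second screening visit in D.5 confirms the "planned on-site treatment regimen: fixed dose (sofosbuvir and ledipasvir" regimen only. Read literally, that item has one value and cannot define the stratum for earlier participants, although D.2 and D.7 clearly count about 50 of them.

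**Conclusion.** The point holds as a modest, assumption-dependent loss of efficiency. The cost in SVR power is about 0 if regimen is not prognostic and about 1 to 5 points in most scenarios with power near or above 70%. With earlier-regimen rates at 70/70/40, it is 7 to 10 points only where new-regimen SVR is 95% to 97% in the intensive arms and 85% to 90% in TAU. Power there is already about 30% to 55%; the no-effect case at 95/95/95 is similar, with power below 20%. The sample-size equivalent for the SVR risk difference is 0% to 38% over the tabulated scenarios. These figures assume an overall alpha of 0.05, 20% loss unrelated to regimen, and regimen set by enrolment order.

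Three stronger readings are not supported:
- A reader might infer bias or false positives. Near-balance rules out material bias, and the test rejects too seldom, not too often.
- A reader might take 10 points as the expected cost. It is one selected case, in a trial underpowered either way, and the documents give no rates that single it out. Nor is it a ceiling.
- A reader might expect stratification to restore 80% power. At 95/95/90, power falls from 0.822 to 0.318 mainly because the arm effect shrinks; stratifying recovers 7 points of that.

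**What to change.** In D.11 and D.12.2, stop choosing covariates by observed baseline imbalance and keep the baseline table as description. For SVR and completion, pre-specify a 2-df CMH test stratified by regimen group (earlier v ledipasvir/sofosbuvir). Stratify the two named pairwise comparisons at 0.025 in the same way, and report regimen-stratified risk differences with confidence intervals.

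Define the group by something fixed before randomisation: the regimen planned at randomisation, or enrolment before v after the switch. Do not use the regimen received. CGT participants may wait for a cycle (D.8.1), so near the switch the regimen received could depend on arm. Reconcile Table 1 and the D.5 screening item, which name only ledipasvir/sofosbuvir, with the 150/100 split in D.2 and D.7.

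The cost is a change of wording, plus confirming that planned regimen or enrolment date is on file for the earlier participants. The statistical downside is about half a point of power if regimen is not prognostic. Little is gained for adherence.
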